8.1 SPECIFICATION OF SAFETY PARAMETERS

8.1.1 DEFINITION OF ADVERSE EVENTS (AE)

Per 21 CFR 312.32(a) an AE is any untoward (unfavorable, harmful, or pathologic) medical occurrence in a subject administered a pharmaceutical (investigational) product even if the event does not necessarily have a

causal relationship with this treatment.

An AE can therefore be any unfavorable and unintended sign (including an abnormal laboratory finding that is deemed clinically significant), symptom, or disease temporally associated with the use of a medicinal (investigational) product whether or not related to the medicinal (investigational) product.

An AE does include any:

- Exacerbation of a pre-existing illness.
- Subjective or objective symptoms spontaneously offered by the subject and/or observed by the investigator or study staff.
- Increase in frequency or intensity of a pre-existing episodic event or condition.
- Condition detected or diagnosed after study drug administration even though it may have been present prior to the start of the study (unless it can be demonstrated by medical record review that the onset of the event preceded the date/time of Informed Consent).
- Continuous persistent disease or symptoms present at baseline that worsen following the start of the study.
- Symptoms associated with disease not previously reported by the subject.
- Untoward medical occurrences considered by the investigator to be related to study-mandated procedures.
- Abnormal assessments (e.g., change on physical examination, ECG findings), if they represent a clinically significant finding, that were not present at Baseline or worsened during the course of the study.
- Laboratory test abnormalities, if they represent a clinically significant finding, symptomatic or not, which were not present at Baseline or worsened during the course of the study.

An AE DOES NOT include a/an:

- Elective medical or surgical procedure (e.g., surgery, endoscopy, tooth extraction, transfusion).
- Pre-existing diseases or conditions present or detected at the start of the study that do not worsen.
- Situations where an untoward medical occurrence has not occurred (e.g., hospitalization for cosmetic elective surgery, social and/or convenience admissions).
- The disease or disorder being studied, or sign or symptom associated with the disease or disorder, unless more severe than expected for the subject's condition.

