8.4.3 ADVERSE EVENTS OF SPECIAL INTEREST

Please note that for an event to be classified as an AE of special interest (AESI), the event should meet the definition of an Adverse Event per [Section 8.1.1](#). Thus, if the investigator considers the event to be an AE, and it meets one or more of the criteria listed below, then the event should be classified as an AESI and

reported according to the timeframe specified.

The following will be considered AEs of special interest (AESI) if they qualify as AEs per the preceding paragraph:

- Clinically significant peripheral edema or pulmonary edema.
- Clinically significant systolic BP >160 but <170 mmHg over consecutive timepoints spanning 30 or more minutes.
- Clinically significant systolic BP <90 or >170 mmHg at a single timepoint.
- Clinically significant diastolic BP >100 but <110 mmHg over consecutive timepoints spanning 30 or more minutes.
- Clinically significant diastolic BP <60 or >110 at a single timepoint.
- A change of >25% from baseline in systolic and/or diastolic BP.
- Reduced kidney function (eGFR < 45 mL/min/1.73 m²).
- Suspected transmission of blood-borne infectious agents.

AESI occurring during the study should be reported within 48 hours of observation or learning of the event, unless the event is serious, in which case the event must be reported according to the timeframes specified in [Section 8.4.2.1](#).

Note: Blood pressures meeting the parameters above that are not considered adverse events need not be reported within the 48-hour window. Rather, these will be considered “blood pressures of special interest” and analyzed separately.

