9.3. Vital Signs

Descriptive summaries of actual values and changes from baseline will be calculated for seated systolic blood pressure, standing systolic blood pressure, and supine systolic blood pressure, seated diastolic blood pressure, standing diastolic blood pressure, and supine diastolic blood pressure, heart rate, respiration rate, and body temperature. These summaries will be presented by visit and treatment group. Vital signs are collected at all study visits. During the infusion periods (Visit 3-Visit 7 and Visit 11- Visit 15), orthostatic vital signs (supine systolic and supine diastolic blood pressure compared to standing systolic and standing diastolic blood pressure) should be measured prior to infusion start and at approximately [REDACTED] after infusion start. Seated systolic and seated diastolic blood pressure is measured at multiple timepoints during and after each infusion. Abnormal vital sign values will be flagged in the listings. Abnormal vital sign values are as follows:

- Seated systolic blood pressure value < 90 mmHg
- Seated systolic blood pressure value > 180 mmHg
- Seated diastolic blood pressure value < 50 mmHg
- Seated diastolic blood pressure value > 110 mmHg
- Incidence of orthostatic hypotension (a decrease in systolic blood pressure of > 20 mm Hg and/or a decrease in diastolic blood pressure of > 10 mm Hg between supine and standing)
- Heart rate > 100 beats per minute
- Temperature > 37.5°C
- Temperature < 36.5°C
- Respiration rate > 20 breaths per minute
- Respiration rate < 12 breaths per minute

The vital sign measurements that meet the criteria for blood pressures of special interest (listed below) will also be identified from the vital signs source data and summarized separately by study visit, timepoint, and treatment.

- Seated systolic blood pressure >180 mmHg
- Seated systolic blood pressure > 200 mmHg
- Seated systolic blood pressure < 90 mmHg
- Seated diastolic blood pressure > 110 mmHg
- Seated diastolic blood pressure > 120 mmHg
- Seated diastolic blood pressure < 50 mmHg
- A change of $\geq 30\%$ from baseline in seated systolic and/or seated diastolic blood pressure

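### The SAP counts blood pressures of special interest on narrower numeric limits than Protocol 8.4.3 sets, and its by-visit table uses a denominator that SAP 4.1 rules out

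*SAP*

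**What the plan says.** Protocol v5.0 Section 8.4.3 lists five blood pressure parameters for adverse events of special interest (AESI). The rule for one systolic measurement is "Clinically significant systolic BP <90 or >170 mmHg at a single timepoint". Diastolic pressure has a matching rule at 60 and 110. Two more parameters cover pressures held for at least half an hour, between 160 and 170 for systolic or between 100 and 110 for diastolic. These four are worded for clinically significant readings. The fifth is not: "A change of >25% from baseline in systolic and/or diastolic BP".

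A Note closes the section. It reads: "Blood pressures meeting the parameters above that are not considered adverse events need not be reported within the 48-hour window". Such measurements become BPSIs instead and get an analysis of their own.

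SAP Section 9.3 defines BPSIs from the vital signs data. Its first item is "Seated systolic blood pressure >180 mmHg", with a further tier above 200 and a low limit of 90. For diastolic pressure, also seated, the limits are below 50, above 110 and above 120. A change of at least 30% in either one counts as well. Table 14.3.6.1.2 and Listing 16.2.8.2.2 repeat that list. SAP Section 10 says that the protocol is going to be amended and that BPSI ranges have been identified. SAP Section 1 names protocol V4.0 of 08MAR2019 as its basis.

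On denominators, SAP Section 4.1 says that by-visit displays use subjects with non-missing data at each visit. The footnote of Table 14.3.6.1.2, which is laid out by visit and timepoint, divides by the Safety Set.

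**The concern.** Both documents use the same term for two different sets of readings. Safety is the primary objective, and v5.0 took non-AE blood pressures out of 48-hour AESI reporting on the understanding that they would be analysed separately. If that analysis applies narrower limits, some readings past the protocol's numbers appear in no BPSI count and carry no flag.

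The denominator matters for a different reason. Counts are unaffected, but percentages at later visits are pulled down as subjects leave, and by different amounts in the two arms if missingness differs.

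**Working it through.** **1. Limits side by side (mmHg)**

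| Parameter | Protocol 8.4.3 | SAP 9.3 | Falls between |
|---|---|---|---|
| Systolic, high, single reading | >170 | >180 (and >200) | 171–180 |
| Systolic, low | <90 | <90 | none |
| Diastolic, high, single reading | >110 | >110 (and >120) | none |
| Diastolic, low | <60 | <50 | 50–59 |
| Change from baseline | >25% | ≥30% | >25% to <30% |
| Systolic, sustained 30 min or more | >160 to <170 | absent | whole band |
| Diastolic, sustained 30 min or more | >100 to <110 | absent | whole band |

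The single-reading and change rules were applied to every whole-number reading over a range of baselines (systolic 100–160, diastolic 60–100). This gave 703 systolic and 357 diastolic baseline–reading pairs that meet the protocol numbers but not the SAP's, and none the other way. Numerically, the SAP set lies wholly inside the protocol set. With baseline systolic 140, for example, the SAP misses 99–104 and 171–180. With baseline diastolic 70 it misses 50–59 and 88–90.

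**2. Versions.** Protocol v5.0 is dated 23SEP2019 and SAP version 4.0 is dated 17-Aug-2020, 329 days later.

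**3. The clinical-significance qualifier.** Four of the five protocol parameters carry it; the change parameter does not. Protocol 8.1.1 counts as adverse events "Abnormal assessments (e.g., change on physical examination, ECG findings), if they represent a clinically significant finding, that were not present at Baseline or worsened". Read literally, a clinically significant reading that is new or worse is already an AE, so for those four parameters almost nothing is left for the Note to send to a separate analysis. Raw vital signs do not record the judgement. For the change parameter, >25% against ≥30% conflicts on any reading.

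**4. Possible size.** The documents give no blood pressure distribution, so every mean and SD here is an assumption, and the qualifier is not applied.

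Missed share = 1 − P(past SAP limit) / P(past protocol limit)

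Each case is run with normal tails and with a t distribution on 4 df scaled to the same SD (scale = SD/√2).

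| Case (mean/SD) | Tail | Past protocol | Past SAP | Missed share |
|---|---|---|---|---|
| Diastolic 75/10 | normal | 6.68% | 0.62% | 90.7% |
| Diastolic 75/10 | t | 5.06% | 1.21% | 76.2% |
| Systolic 130/17 | normal | 0.931% | 0.163% | 82.4% |
| Systolic 130/17 | t | 1.459% | 0.708% | 51.5% |
| Change 0/12 (%, two-sided) | normal | – | – | 66.6% |
| Change 0/12 (%, two-sided) | t | – | – | 42.8% |

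Ranges over wider assumptions:

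- Low diastolic (mean 70–80, SD 9–12): 76–97% normal, 69–82% t.
- High systolic (mean 120–140, SD 15–20): 66–93% normal, 45–59% t.
- Percent change (mean 0, SD 8–18): 42–90% normal, 36–47% t.

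Some missed readings would be caught by the ≥30% row. Simulating correlated baseline and follow-up values with a percent-change SD of 12 to 15 lowers diastolic 75/10 from 91% to 89–83% (normal) and from 76% to 70–65% (t). Systolic 130/17 falls from 82% to 79–67% (normal) and from 52% to 46–40% (t).

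As a share of all readings these are smaller: 6.68 − 0.62 = 6.06% for diastolic 75/10 and 0.931 − 0.163 = 0.77% for systolic 130/17 (normal tails, before overlap).

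**5. Denominator.** The protocol assumes 25% drop-out; 90 × 0.75 = 67.5 reproduces its figure of about 68 evaluable subjects. If 25% of the Safety Set had no data at some later visit, a true 20% rate would print as 0.20 × 0.75 = 15%. With assumed losses of 20% on GRF6021 and 35% on placebo, overall loss is (60 × 0.20 + 30 × 0.35)/90 = 25%, and equal 20% rates print as 0.20 × 0.80 = 16% and 0.20 × 0.65 = 13%. Shells 14.2.4.1, 14.2.7.1, 14.2.8.7, 14.3.5.3.3 and 14.3.6.2.2 have the same fault.

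**The case against.** The strongest reply is that only the change parameter conflicts literally. The other mismatches appear once the clinical-significance qualifier is set aside. That is correct, and it limits how the conflict should be described. But keeping the qualifier strictly would leave the Note almost nothing to analyse for the other four parameters, so the text needs clarifying either way.

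Second, SAP Section 10 discloses that BPSI ranges were identified, the document history shows this was before v5.0 existed, and the protocol leaves analytical detail to the SAP. The disclosure is real. It gives no reason to depart from the parameters that v5.0 then fixed, and SAP versions 3.0 and 4.0 both came after that amendment. A diastolic limit of 50 does occur in Protocol Appendix 11 Table 3, but for sustained hypotension during infusion, not for BPSIs.

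Third, nothing is lost: seated pressures are summarised with change from baseline, plotted and listed, and the size estimates rest on assumed distributions with small base rates for high systolic readings. All of this stands. It bears on importance, not on whether the definitions agree.

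On the denominator, the phrase allowing exceptions in SAP 4.1 belongs to the general sentence, not the by-visit one. The 25% is loss between randomization and evaluability, so it only illustrates later-visit loss. It cannot be carried to the Evaluable Set shells, whose members all completed Visit 8.

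**Conclusion.** The concern holds and should be fixed before lock. The SAP's numeric BPSI limits are a strict subset of the protocol's: three thresholds are narrower, two sustained bands are missing and two limits agree. The change parameter conflicts outright. For the other four, the numbers conflict and the protocol's Note is itself unclear.

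How many readings are affected cannot be stated. The range of about one third to over 90% of readings past the protocol numbers depends entirely on the assumed spread and tail shape, and allowing for the ≥30% row reduces the diastolic and systolic shares. The consequence is confined to a descriptive safety table and a listing flag. The TEAE/SAE endpoint and the AESI table do not change.

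The denominator conflict also holds, as a secondary point: counts stand, later-visit percentages are understated, and the arm comparison is distorted only if missingness differs by arm.

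**What to change.** - Reconcile SAP 9.3 with Protocol 8.4.3, base the SAP on protocol v5.0, and state whether and how clinical significance applies to BPSIs. Which limits are clinically right is not a matter for this review.
- Add rows to Table 14.3.6.1.2 and flags to Listing 16.2.8.2.2 for each numeric 8.4.3 parameter, including both sustained bands. Keep the existing SAP tiers. Footnote that the clinical-significance judgement is not applied to these rows.
- Say whether BPSIs are limited to seated readings, since 8.4.3 names no position. Define when consecutive readings span 30 minutes, given the ±5-minute tolerance in Appendix 11.
- Mark or separate readings already reported as AEs, matching on subject, date and time to the blood-pressure AEs that SAP 9.1.3 identifies before lock. Matching will be imperfect where AE times are imputed; say so.
- Divide by subjects with non-missing data at the visit in Table 14.3.6.1.2 and the five other shells named above.
- Correct the source line of Table 14.3.6.1.2, which points to the urinalysis listing (16.2.8.1.3) rather than the blood pressure listing (16.2.8.2.2).

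The cost is SAP wording, footnotes, and some programming for the added rows, flags and AE matching. Seated pressure is already recorded every 15 to 30 minutes during infusion, so no new data are required.

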9.4. Electrocardiograms (ECGs)

12-Lead Electrocardiograms will be obtained at Screening, Week 1 (Visit 7) and Week 13 (Visits 11 and 15).

Descriptive summaries will be presented for ECG measures of QT interval, QTc interval, and HR. Corrected QTc intervals will be calculated using Fridericia's correction formula. These summaries will be presented by treatment group and visit.

The number and percentage of subjects with normal, abnormal but not clinically significant, and abnormal and clinically significant ECG results will be summarized for the Safety Dataset by treatment group and visit.

9.5. Further Safety Evaluations

9.5.1. Physical Examination

A full physical examination will be performed to assess the following organ systems: skin; ears, nose, and throat (ENT); head; eyes; lungs/chest; heart; abdomen; musculoskeletal; extremities; neurologic system; and lymphatic system. The neurological exam will include cranial nerves (visual fields, fundoscopic exam, pupillary light reflex, extraocular muscles, facial sensation and symmetry, palate and tongue, and head turning and shoulder shrug); muscle strength, tone, and bulk; reflexes (biceps, triceps, knees, ankles, and plantar); coordination (finger-to-nose, heel-knee-shin); sensory function (light touch and pinprick); and gait. Height will be measured at screening and weight will be monitored during the trial.

While the subject is inpatient, a targeted physical exam, including auscultation of the heart and lungs, an assessment of peripheral edema, and weight, will be performed per the study schedule.

All physical exam results will be listed.

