GRF6021 is contraindicated in patients with severe anemia, congestive heart failure, or increased blood volume (PI) and these are exclusion criteria in this study. GRF6021 is depleted of the majority of immunogenic proteins during the manufacturing process, and thus is not expected to alter the blood typing characteristics of the recipient and should not sensitize humans to its subsequent administration [REDACTED]. ABO antigen typing is not required prior to administration. GRF6021 is not expected to significantly alter the urinalyses of recipients, their bleeding times, coagulation times, prothrombin times, prothrombin consumption, platelet counts, or fibrinogen levels when given in quantities of up to 1000 mL [REDACTED].

Based on the cumulative review [REDACTED] (PSUR), the production steps taken to increase the safety margin and avoid virus transmissions, and the multiple safety minimization steps implemented in this study, the benefit-risk balance for GRF6021 as an investigative product in PD-MCI and PDD is favorable.

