 4. MDS-UPDRS 1/2/3
 5. SE-ADL
 6. CISI-PD
 7. PDQ-39
 8. GDS-15

7.3.4 TREATMENT

There are two treatment periods scheduled during the trial. During each treatment period, subjects will receive a total of 5 infusions of their assigned treatment (i.e., either GRF6021 or placebo). It is anticipated that sites will infuse subjects with 5 doses over 5 consecutive days. A “grace day” is allowed in the event of unanticipated safety or health concerns during each treatment period.

Visits 3-7 (Days 1-5) and 11-15 (Day 85*-89):

*Day 85 has a \pm 7-day window

- Perform the following procedures prior to administering study treatment:
 - Review AEs and concomitant medications.
 - Obtain blood and urine samples for Comprehensive Labs (**Visits 6 and 14 Only**); fasting samples preferred.
 - Obtain samples for proteomics/epigenetics/biobanking; fasting samples preferred (**Visits 3 and 11 Only**).
 - Obtain sample for ApoE testing (**Visit 3 Only**).
 - For WOCBP Only: perform pregnancy testing and review results (**Visits 3 and 11 Only**).
 - Obtain Pre-infusion Safety Lab samples and assess results **prior to the next day’s infusion (Visits 3, 4, 6, 11, 12, and 14 Only)**. When using an i-STAT Handheld Blood Analyzer, the blood sample(s) may be obtained on the same day as the infusion (Visits 4, 5, 7, 12, 13, and 15).
 - Perform targeted physical exam (i.e. auscultation of heart and lungs and assessment of peripheral edema) (**Visits 3, 5, 7, 11, 13, and 15 Only**).
 - Measure body weight in kilograms.
 - Perform 12-lead ECG (**Visit 7, 11, and 15 Only**).
 - Administer the S-STS (**Visit 3 Only**).
 - Collect vital signs (including sitting, supine, and standing BP).
- Administer study treatment and perform safety assessments per the Infusion Administration Manual ([Appendix 11](#)).
- Administer the S-STS after the subject’s final infusion (**Visit 7 Only**).

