10.4.4 ANALYSIS OF THE SECONDARY SAFETY ENDPOINTS

Actual values and changes from baseline in clinical laboratory measurements, vital signs, body weight, and S-STS scores will also be assessed and summarized. Abnormal lab or vital sign values will be determined and flagged in the listings. Laboratory shift tables or graphics displaying the change (number of subjects) relative to the reference range from baseline to each study visit may also be presented for each test. The investigator should exercise his or her medical and scientific judgment in deciding and documenting whether an abnormal laboratory finding, or other abnormal assessment is clinically significant.

For secondary safety endpoints that are continuous in nature (e.g. clinical laboratory parameters, systolic and diastolic BP, heart rate, respiratory rate, body temperature, body weight, S-STS score) the mean, median, minimum, maximum, and standard deviation will be plotted over time.

For secondary safety endpoints that are categorical in nature (e.g. physical exam or ECG abnormalities), the frequency counts and percentages will be presented as a descriptive summary.

Per-subject extent of exposure will be listed.

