14.3.6 Other Safety Data Summary Tables				
Table 14.3.6.1.1	Safety	Summary of Vital Signs by Study Visit and Treatment	X	
Table 14.3.6.1.2	Safety	Summary of Blood Pressures of Special Interest by Study Visit and Treatment	X	
Table 14.3.6.2.1	Safety	Summary of 12-Lead Electrocardiogram by Study Visit and Treatment		
Table 14.3.6.2.2	Safety	Summary of 12-Lead Electrocardiogram Interpretation by Study Visit and Treatment		
Table 14.3.6.3	Safety	Summary of Sheehan-Suicidality Tracking Scale (S-STSS) by Study Visit and Treatment	X	
Table 14.3.6.4	Safety	Summary of Concomitant Medications by ATC Class Level 4, PT, and Treatment		

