16.2.8 Laboratory Values and Other Clinical Observations and Measurements (by Subject)		
Listing 16.2.8.1.1	All Subjects	Clinical Laboratory Data: Hematology
Listing 16.2.8.1.2	All Subjects	Clinical Laboratory Data: Serum Chemistry
Listing 16.2.8.1.3	All Subjects	Clinical Laboratory Data: Urinalysis
Listing 16.2.8.1.4	All Subjects	Clinical Laboratory Data: Urine Drug Screen and Pregnancy Tests
Listing 16.2.8.1.5	All Subjects	Clinical Laboratory Data: Coagulation
Listing 16.2.8.1.6	All Subjects	Clinical Laboratory Data: Immunology
Listing 16.2.8.1.7	All Subjects	Clinical Laboratory Data: Serology
Listing 16.2.8.2.1	All Subjects	Vital Signs
Listing 16.2.8.2.2	All Subjects	Blood Pressure
Listing 16.2.8.3	All Subjects	12-Lead Electrocardiogram (ECG) Results
Listing 16.2.8.4	All Subjects	Echocardiogram Results
Listing 16.2.8.5.1	All Subjects	Physical Examination
Listing 16.2.8.5.2	All Subjects	Targeted Physical Examination
Listing 16.2.8.6	All Subjects	S-STS
Listing 16.2.8.7	All Subjects	Prior and Concomitant Medications

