		XXX	DDMMYYYY/HH:MM (XX)	XXXXXXXX;XXXX	XXX	XXX	XXX
		XXX	DDMMYYYY/HH:MM (XX)	XXXXXXXXXXXX	XXX	XXX	XXX
		XX	DDMMYYYY/HH:MM (XX)	XXXXXXXXXXXX	XXX	XXX	XXX
		XXX	DDMMYYYY/HH:MM (XX) ND	XXXXXXXXXXXX	XXX	XXX	XXX
XXXXXX	XXXXXX	XXX	DDMMYYYY/HH:MM (XX)	XXXXXXXXXXXX	XXX	XXX	XXX
		XXX	DDMMYYYY/HH:MM (XX)	XXXXXXXXXXXX	XXXX	XXXX	XXXX

Abbreviation: ND = not done.
 Note: Study day is calculated relative to the date of first dose.
 [1] Treatment is based on treatment received.

Programming note: If ECG was not performed, concatenate with reason.

Statistical Analysis Plan,
 Sponsor Alkermes, Inc.
 Protocol Number ALK602.1-201
 PCN Number ALKA7951

Listing 16.2.8.5.1
 Physical Examination
 All Subjects

Subject ID	Treatment [1]	Was Physical Exam performed?	Date/Time Performed (Study Day)	Body System	Result	Reason Not Done	If Abnormal, Describe
XXXXXX	XXXXXXX	XXX	DDMMYY/HH:MM (-X)	General Appearance	Normal		
				Skin	Abnormal, CS		XXXXXXXXXX
				Head and Neck	Normal		
				Lymph Nodes	Normal		
				Thyroid	Normal		
				Musculoskeletal	Normal		
				Extremities	Normal		
				Cardiovascular	Normal		
				Lungs	Normal		
				Abdomen	Normal		
				Neurological	Normal		

Abbreviations: CS = clinically significant; NCS = not clinically significant.
 Note: Study day is calculated relative to the date of first dose.
 [1] Treatment is based on treatment received.

Programming Note: If Exam was not performed, concatenate reason.

Listing 16.2.8.5.2
 Targeted Physical Examination
 All Subjects

Same shell as Listing 16.2.8.4.1. Body Systems will be: Heart, Lungs, and Peripheral Edema.

Statistical Analysis Plan,
 Sponsor Alkermes, Inc.
 Protocol Number ALK6021-201
 PCN Number ALKA7951

Listing 16.2.8.6
 S-STS
 All Subjects

Subject ID	Treatment [1]	Was Questionnaire Collected?	Date/Time Collected (Study Day)	Total Scale Score
XXXXXX	XXXXXX	XXX	DDMMYYYY/ HH:MM (XX)	XX

Abbreviation: S-STS = Sheehan Suicidality Tracking Scale.
 Note: Study day is calculated relative to the date of first dose.
 [1] Treatment is based on treatment received.

Programming Note: if questionnaire was not collected, concatenate reason.

Statistical Analysis Plan,
 Sponsor Alkermes, Inc.
 Protocol Number ALK6021-201
 PCN Number ALKA7951

Listing 16.2.8.7
 Prior and Concomitant Medications
 All Subjects

[figure not shown]

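### Protocol 10.4.4 commits to counts and percentages of physical exam abnormalities; the SAP only lists them and does not declare the change, so targeted-exam findings not reported as AEs or AESIs are not summarised by arm

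*SAP*

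**What the plan says.** Protocol 10.4.4 covers safety data of this type directly: "For secondary safety endpoints that are categorical in nature (e.g. physical exam or ECG abnormalities), the frequency counts and percentages will be presented". The targeted exam in Protocol 7.3.4 consists of "auscultation of heart and lungs and assessment of peripheral edema", done before the infusion at Visits 3, 5, 7, 11, 13 and 15. A full physical exam is done at screening and at end of study or early termination.

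The opening of SAP Section 9 says safety will be evaluated from ECG and physical examination results as well as the named endpoints. For ECG, SAP 9.4 and Table 4 follow through with "Summary of 12-Lead Electrocardiogram Interpretation by Study Visit and Treatment" (Table 14.3.6.2.2). For examinations, SAP 9.5.1 ends with "All physical exam results will be listed". Table 5 has one listing for the full exam (16.2.8.5.1) and one titled "Targeted Physical Examination" (16.2.8.5.2). The shell of the second specifies "Body Systems will be: Heart, Lungs, and Peripheral Edema". SAP Section 10, on changes from the planned analysis, deals only with blood pressures of special interest.

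**The concern.** The protocol makes a definite commitment, and the SAP replaces it with a weaker output without saying so. Protocol 10.4.4 words laboratory shift tables as optional, but the counts for categorical data are not optional.

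Safety and tolerability is the primary objective. Protocol 2.3.1 states that the product is contraindicated in congestive heart failure and raised blood volume, and exclusion criterion 7 removes subjects with signs of hypervolemia, including edema. New edema or abnormal lung findings during a five-day course are therefore relevant to tolerability. The targeted exam records them repeatedly in both arms, but a reader of the study report would have no count, denominator or change from the pre-dose exam for findings that were not also reported as adverse events.

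**Working it through.** The point rests mainly on comparing the documents; the only arithmetic is a count of exams.

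**Step 1. Commitment against planned output**

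- ECG: promised in Protocol 10.4.4. The SAP gives Table 14.3.6.2.1 (measurements) and Table 14.3.6.2.2 (interpretation), both by visit and treatment.
- Physical exam: promised in the same sentence. SAP Table 4 has no exam table, Table 6 has no exam figure, and Table 5 has two listings.
- Declared change: SAP Section 10 does not mention it.
- Version effect: the SAP cites protocol version 4.0, while the current protocol is 5.0. The protocol's revision history shows no change to 10.4.4 in the 5.0 update, so the difference is not explained by versions.

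**Step 2. What still reaches a by-arm table**

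- Protocol 8.1.1: a clinically significant change on examination is an AE, and so are signs observed by study staff.
- Protocol 8.4.3: clinically significant peripheral or pulmonary edema is an AESI if it qualifies as an AE.
- SAP Table 4: TEAEs (14.3.1.2, and 14.3.1.3 by severity) and AESIs (14.3.2.3) are tabulated by SOC, PT and treatment.
- Body weight, which SAP 9.5.1 includes in the targeted exam, is summarised with change from baseline by visit and arm in Table 14.3.6.1.1.

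What is left without an arm summary is the set of heart, lung and edema exam results not reported as any AE.

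**Step 3. How many exams**

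Inputs: about 60 subjects on GRF6021 and 30 on placebo (Protocol 10.5), and six exam visits (Protocol 7.3.4). Exams = visits × subjects.

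- All six visits: 6 × 60 = 360 and 6 × 30 = 180.
- Visit 3 is before the first infusion and serves as baseline. After the first dose: 5 × 60 = 300 and 5 × 30 = 150.
- If Visit 11 is the reference for course 2, Visits 5, 7, 13 and 15 remain as within-course comparisons: 4 × 60 = 240 and 4 × 30 = 120.

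These are upper limits. They assume every subject attends every visit, and the protocol itself allows for 25% drop-out.

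**Step 4. Whether the data support a table**

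The shell of Listing 16.2.8.5.1 records results as normal or abnormal, the latter marked clinically significant or not, with free text. The targeted-exam listing refers to the shell of a Listing 16.2.8.4.1, which is not in Table 5; I take this to mean 16.2.8.5.1. Those three categories are the same as in the ECG interpretation table. There is no grade for edema, so worsening within a category cannot be derived.

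**The case against.** The best case for leaving the plan alone has four parts.

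First, important findings are already compared: they become AEs or AESIs and are tabulated by treatment. This stands, and it sets the limit of the point. A reader might infer that the edema and lung checks are never compared by arm, and the documents do not support that. Mild findings can also be AEs, since Protocol 8.2.1 defines mild as easily tolerated. What remains depends on the investigator's decision to report. For blood pressure, another item on the AESI list, the sponsor did not rely on that decision alone: Protocol 8.4.3 has readings that are not AEs analysed separately, and SAP 9.3 gives them their own by-arm table. Edema, first on that list, has no equivalent.

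Second, physical examination is not among the listed secondary safety endpoints in Protocol 4.2.2. That is true, but ECG is not listed there either, and it is tabulated.

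Third, weight and vital signs by arm already bear on fluid status. They do, but they do not replace edema or auscultation findings.

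Fourth, the listings are sorted by treatment (SAP 13.4), so the information is available. A listing still gives no counts or percentages, which is what the protocol promised.

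A reader might also infer that the targeted exam is designated as volume-overload monitoring. No section says so; it is a reasonable inference from the exam's content and from the contraindication and exclusion criteria. Nor can all six exams show a treatment effect, because Visit 3 precedes dosing.

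**Conclusion.** The mismatch holds: a commitment in Protocol 10.4.4 is met for ECG and not for physical examination, and SAP Section 10 does not say so. The consequence is limited to targeted-exam findings in heart, lungs and peripheral edema that are not reported as AEs or AESIs. These have no summary by arm. The material affected is five post-first-dose exams per subject, at most about 300 on GRF6021 and 150 on placebo, with Visit 3 as the pre-dose baseline.

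This rests on the planned arm sizes, full attendance, and the targeted exam being recorded in the same categories as the full exam. The documents give no expected rate of abnormal findings, so I make no claim about how large a difference might go unnoticed. No primary or listed secondary endpoint changes. The point is worth correcting because safety is the primary objective and the promised summary is cheap to produce.

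**What to change.** Add one Safety Set table by arm and visit, giving counts and percentages of targeted-exam results for heart, lungs and peripheral edema as normal, abnormal NCS or abnormal CS. Model it on ECG Table 14.3.6.2.2. Include a row for subjects with any shift to a worse category from the pre-dose Visit 3 exam, and from the Visit 11 exam for course 2. Give the same counts for the end-of-study full exam against screening. Amend SAP 9.5.1 and Table 4 to match.

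The counts and percentages meet the protocol's wording. The shift row goes slightly further, but it can be derived from the recorded categories. Confidence intervals are not needed to meet the commitment.

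The cost is one extra descriptive table from data already collected, with no protocol amendment. If the sponsor prefers listings only, SAP Section 10 should state the departure and the reason. That would resolve the inconsistency but leave these findings unsummarised.
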